8.1 Adverse events

This analysis will be conducted in the ITT population. The number and proportion of participants with adverse events that occur in up to 0.5% of the study population will be presented by the study arm.

Adverse events categorized by the treating physician to be related to the treatment will also be listed by the study arm, regardless of their frequency. These will include, but are not limited to, vaginal bleeding, epigastric pain, and heartburn.

Table shell 5. Adverse events

Adverse events	LDA, n(%)	Placebo, n(%)	Overall
Total			
Listed			

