8.0 ADVERSE EVENTS AND REPORTING REQUIREMENTS

8.1 Adverse Events (AEs)

- ❖ An adverse event is the appearance or worsening of any undesirable sign, symptom, or medical condition occurring after starting the study drug even if the event is not considered to be related to study drug. Study drugs include the investigational drug/placebo under evaluation that is given during the treatment phase of the study.
- ❖ *Medical conditions/diseases present before starting study drug are only considered adverse events if they worsen after starting study drug.*
- ❖ Abnormal laboratory values or test results constitute adverse events only if they induce clinical signs or symptoms, or are considered clinically significant, or require therapy.

Clinical signs and symptoms will be assessed at baseline, before dosing and all follow-up visits, and recorded on the CRF. Any symptom that worsens or starts after baseline will be recorded as a new adverse event on the e-CRF.

The occurrence of adverse events, such as weakness, chills/rigors, headache, myalgia, dizziness, epigastric pain, abdominal pain, anorexia, nausea, vomiting, diarrhea, palpitations, insomnia, pruritus, coughing, tinnitus, abnormal gait, tremor, clonus or dyskinesia, will be sought by the investigator (or designee) at each study visit and recorded in the e-CRF.

Adverse events also may be detected when they are volunteered by the patient during or between visits or through physical examination, laboratory test, or other assessments.

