9.2 Data Management and Analysis

DATA ANALYSIS; POPULATIONS FOR ANALYSIS

The assignment of patients into analysis populations will be performed prior to database lock and any data analysis.

Randomised – all patients who receive a randomisation number.

Intention-to-treat (ITT) – all randomized patients with at least one relevant post-baseline efficacy assessment, and who had at least one dose of study drug. Following the intention-to-treat principle, patients will be analyzed according to the treatment they were assigned to at randomization.

Primary Analysis (PA) – all ITT patients that completed 36 weeks or delivery

Per Protocol (PP) – all PP patients that meet all of the following:

- Took at least 80% of scheduled study drug

Safety – all patients that received at least one dose of study drug and had at least one post-baseline safety assessment. Patients will be analyzed according to treatment received.

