5.2 Analysis Populations

5.2.1 Intention to Treat (ITT) population

- The intention to treat population refers to all subjects who were randomised. Following the intention-to-treat principle, patients will be analysed according to the treatment they were assigned to at randomization.

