8.2 Serious Adverse Events (SAEs)

A Serious Adverse Event (SAE) is defined as an event which:

- is fatal or life-threatening
- results in persistent or significant disability/incapacity
- constitutes a congenital anomaly/birth defect
- requires inpatient hospitalization or prolongation of existing hospitalization, unless hospitalization is for:
 - routine treatment or monitoring of the studied indication, not associated with any deterioration in condition.
 - elective or pre-planned treatment for a pre-existing condition that is unrelated to the indication under study and has not worsened since the start of study drug.
 - treatment on an emergency outpatient basis for an event not fulfilling any of the definitions of a SAE given above and not resulting in hospital admission.
 - social reasons and respite care in the absence of any deterioration in the patient's general condition.
- is medically significant, i.e., defined as an event that jeopardizes the patient or may require medical or surgical intervention to prevent one of the outcomes listed above

The number and proportion of participants who experience SAEs will be analysed and presented. The appropriate grading of severity of the SAEs will also be presented in counts and proportion. A listing of SAEs experienced will be included per participant.

If any serious adverse events occur in >5% of individuals who receive either intervention, the time to occurrence of the adverse event will be summarized using median (IQR) and graphically with Kaplan-Meier curves.

Table shell 6. Serious adverse events – summary

SAE	LDA, n(%)	Placebo, n(%)	Overall
Total			
Listed			

Table shell 7. Serious adverse events – list

record_id	SAE	Relationship	Comments including action taken

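### SAP 8.1 puts adverse events in the all-randomised, as-assigned set instead of the protocol's as-treated Safety population, which can lower absolute event rates and misplace wrong-kit exposure

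*SAP*

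**What the plan says.** SAP 8.1 fixes the population for adverse events in one sentence: "This analysis will be conducted in the ITT population". That is the only analysis set the SAP defines. Under SAP 5.2.1, "The intention to treat population refers to all subjects who were randomised", and "patients will be analysed according to the treatment they were assigned to at randomization". No condition on dosing or follow-up is attached.

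Protocol 9.2 has a separate Safety set: "all patients that received at least one dose of study drug and had at least one post-baseline safety assessment". Its grouping rule also differs: "Patients will be analyzed according to treatment received". Even the protocol's own ITT set is narrower than the SAP's, being limited to "all randomized patients with at least one relevant post-baseline efficacy assessment, and who had at least one dose of study drug".

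SAP 8.2 does not say which women form the denominator for serious adverse event (SAE) counts. Its rule for adding a time-to-event summary begins "If any serious adverse events occur in >5% of individuals who receive either intervention", which is worded around women exposed rather than women randomised.

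SAP 12.1 lists the main departures from the protocol's analysis section. It mentions neither the loss of the Safety set nor the wider ITT definition. SAP 6.2 adds that, because analysis is by ITT, protocol deviations will not change the approach.

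**The concern.** Protocol 8.1 defines an adverse event as something "occurring after starting the study drug even if the event is not considered to be related to study drug". On that definition a randomised woman who never takes a tablet has no exposure period in which an event could count. A woman who never returns is largely unobserved, since events are mainly sought at visits. If either is entered as having had no event, she enlarges the denominator without having contributed safety information.

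For efficacy, keeping such women in is the cautious choice. For harm it works the other way: absolute rates and risk differences look smaller than they are among exposed women. As-assigned grouping adds a second effect, because an event in a woman who took the other arm's product is credited to the wrong product.

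Both situations are foreseen: Protocol 11.1 gives untreated and wrongly treated women as examples of violations. At stake is how accurately the trial describes the tolerability of a drug given in pregnancy, and whether a programmer can tell which denominator section 8 of the SAP requires.

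**Working it through.** The documents state no figure for never-dosed women, wrong kits or adverse-event rates, so there is no planned figure to reproduce on this point. The check is a comparison of definitions followed by a sensitivity calculation.

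**Inputs**
- Randomised women per arm: 476 / 2 = 238 (SAP 3.1, 1:1 allocation).
- Event rates among evaluable women: 10% on LDA and 5% on placebo (assumed, for illustration).
- k = women per arm who are never dosed or have no safety follow-up and are counted as event-free (assumed; range shown). f = k / 238.

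**Dilution**

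Reported rate = p × (238 - k) / 238 = p × (1 - f), where p is the rate among the 238 - k evaluable women. With the same f in both arms, the risk difference is also multiplied by (1 - f), and the factor cancels from the risk ratio. If the women concerned are all in the LDA arm, the risk ratio becomes 2.00 × (1 - f).

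| k of 238 | f | LDA | Placebo | Difference (points) | RR, equal f | RR, f in LDA only |
|---|---|---|---|---|---|---|
| 0 | 0 | 10.0% | 5.0% | 5.00 | 2.00 | 2.00 |
| 2 | 0.8% | 9.9% | 5.0% | 4.96 | 2.00 | 1.98 |
| 5 | 2.1% | 9.8% | 4.9% | 4.89 | 2.00 | 1.96 |
| 12 | 5.0% | 9.5% | 4.7% | 4.75 | 2.00 | 1.90 |
| 24 | 10.1% | 9.0% | 4.5% | 4.50 | 2.00 | 1.80 |

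The placebo and difference columns take the same f in both arms. If the women concerned were all in the placebo arm, the ratio would rise instead: at k = 24, 10.0 / 4.50 = 2.22.

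**Wrong kit**

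Let a share m of each arm take the other arm's product. The as-assigned rates are 10(1 - m) + 5m for LDA and 5(1 - m) + 10m for placebo.
- m = 1%: 9.95% against 5.05%, ratio 1.97.
- m = 2%: 9.90% against 5.10%, ratio 1.94.
- m = 5%: 9.75% against 5.25%, ratio 1.86.

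Here the ratio as well as the difference moves towards no effect.

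**The 5% trigger in SAP 8.2, read per arm**

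With all 238 women in the denominator, 12 must be affected (12/238 = 5.04%; 11/238 = 4.62%). With 214 exposed, 11 are enough (11/214 = 5.14%). With 226 or more exposed, 12 are still needed (11/226 = 4.87%). The choice of denominator therefore changes the trigger only towards the top of the assumed range.

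**The case against.** Several counter-arguments have force.

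- **Never-dosed women are not strictly barred from the numerator.** Besides the definition quoted above, Protocol 8.1 also has any symptom arising or worsening after baseline recorded as an adverse event. Protocol 8.3 covers all enrolled participants and has everything recorded after baseline summarised. A reader might infer from the definition alone that a never-dosed woman can only inflate the denominator. The recording rules do not support that for a woman who attends visits. This stands.
- **Women with no data may be treated as missing.** SAP 5.4 does not impute endpoints and reports each denominator, and SAP section 6 bases percentages on non-missing observations. If that is applied to adverse events, the dilution from women who never return shrinks or disappears. This stands in part: SAP 8.1 does not say so, and the rule would not correct wrong-kit grouping or address a never-dosed woman who does attend.
- **f may be very small.** Protocol 5.2 has the first pack handed over at the enrollment visit. That does not prove ingestion, but it makes a large never-dosed share unlikely. This stands.
- **ITT for some harms is declared.** SAP 2.2 lists vaginal bleeding, epigastric pain and heartburn as secondary endpoints analysed by ITT, and Protocol 9.3 specifies ITT in general. SAP 12.1 claims to list only the main changes. This weakens any suggestion of concealment. It does not reconcile SAP 8.1 with the safety set in Protocol 9.2.
- **An as-treated set is not protected by randomisation.** Correct, and it is the reason to keep the ITT table alongside.

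Two further inferences are not supported. One is that all harm rates in the trial are diluted: SAP 8.2 assigns no population to SAE counts, so the fault there is ambiguity. The other is that confidence bounds on rare events would be too tight: Table shell 5 plans counts and percentages only.

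**Conclusion.** The conflict between protocol and SAP is real. The protocol's Safety population is gone from the SAP, adverse events are moved to all randomised women as assigned, the move is not recorded, and the SAE denominator is left open.

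The numerical consequence is conditional. It requires that some women are never dosed or have no safety follow-up, and that they are counted as event-free. Absolute rates and risk differences then fall by the factor (1 - f): about 1% of their value at an assumed f of 1%, and about 10% at an assumed 10%. At f = 0 there is no effect. A reader might conclude that the plan biases the comparison of harms towards no difference on every scale. That does not follow: with equal f the risk ratio is untouched, and with unequal f it can move either way. Only wrong-kit exposure pulls the ratio towards 1, and the documents give no estimate of its frequency.

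The point does not touch the primary efficacy analysis. It is worth correcting because the protocol already contains the appropriate safety set and the records needed to build it are already planned.

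**What to change.** - Restore the protocol's Safety population in SAP 5.2. Use it, by treatment received, for the counts and percentages in 8.1 and 8.2 and for the 5% trigger in 8.2.
- State that women with no post-baseline safety data are not counted as event-free, and report how many there are by arm.
- Keep the all-randomised, as-assigned table as supplementary. It also meets the ITT commitment in SAP 2.2 for vaginal bleeding, epigastric pain and heartburn.
- Report the numbers never dosed and given a wrong kit, by arm.
- Record any remaining departure from Protocol 9.2 in SAP 12.1, including the wider ITT definition.

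The cost is a few sentences in the SAP, a derived population flag with actual treatment, and one additional table. The enrollment form records whether drug was given, the follow-up form records pill counts and adherence, and the drug accountability form records the kit code. No new data collection is needed.

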8.2 Relationship of AE to study product

The investigator must determine the relationship of the AE to the product under investigation and document in the appropriate section of the e-CRF. For each AE, an assessment of the relatedness to the study drugs should be made using the following scale:

- **Unrelated:** Onset of the AE had no reasonable temporal relationship to administration of the study product or a causal relationship to administration of the study product is biologically implausible or the event is attributed to an alternative etiology.

- **Possibly Related:** Onset of the AE has a reasonable temporal relationship to study product administration and a causal relationship is not biologically implausible.
- **Probably Related:** Onset of the AE has a strong temporal relationship to administration of the study product that cannot be explained by the participant's clinical state or other factors and a causal relationship is not biologically implausible.
- **Definitely Related:** Onset of the AE shows a distinct temporal relationship to administration of the study product that cannot be explained by the participant's clinical state or other factors or the AE occurs on re-challenge or the AE is a known reaction to the product or chemical group or can be predicted by the product's pharmacology.

These criteria in addition to good clinical judgement should be used as a guide for determining the causal assessment. If it is felt that the event is not related to study drug therapy, then an alternative explanation should be provided.

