8.3 Reporting Adverse Events

Study site coordinators will document on the appropriate study e-CRF all AEs reported by or observed in enrolled study participants regardless of severity and presumed relationship to study product. The study clinician must provide on this form information on symptoms, time of onset, severity, frequency, product-relatedness, actions taken and participant outcome. The PI may request additional information from the site if it is needed to evaluate the AE. Site coordinators will report information on SAEs to the local Ethics committee in accordance with the local committee requirements.

All adverse events must be recorded on the e-CRF with the following information:

1. the severity grade (mild, moderate, severe)
2. its relationship to the study drug(s) (see section 8.2)
3. its duration (start and end dates or if continuing at final exam)
4. whether it constitutes a serious adverse event (SAE)

- All adverse events recorded at any time after baseline on the CRF will be summarized at analysis.

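### SAP 8.1 words its adverse-event table threshold as a ceiling of 0.5%, very probably a slip for a minimum; followed literally, the more frequent unrelated, non-serious events lose their own by-arm rows

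*SAP*

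**What the plan says.** SAP 8.1 analyses adverse events in the ITT population and gives the rule for the by-arm table: "participants with adverse events that occur in up to 0.5% of the study population will be presented by the study arm". The sentence after it reads: "Adverse events categorized by the treating physician to be related to the treatment will also be listed by the study arm, regardless of their frequency". Table shell 5 has columns for LDA, placebo and overall. Its rows are 'Total', which is not defined, and the listed event terms.

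SAP 5.2.1 fixes the population: "The intention to treat population refers to all subjects who were randomised". SAP 3.1 plans 476 women, allocated 1:1.

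SAP 8.2 covers serious events separately, with a by-arm summary and a listing that have no frequency cut-off. Its one percentage rule, for time-to-event displays, is a minimum: "If any serious adverse events occur in >5% of individuals who receive either intervention".

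Protocol 8.3 commits to a full summary: "All adverse events recorded at any time after baseline on the CRF will be summarized at analysis". Protocol 8.1 names a set of symptoms that "will be sought by the investigator (or designee) at each study visit and recorded in the e-CRF".

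**The concern.** 'Up to' sets a maximum. A table built to that rule keeps the rarest events and leaves out the more frequent ones, the reverse of what a frequency cut-off in a safety table is normally for.

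Tolerability is one of the stated purposes of the trial (Protocol 1.2). For non-serious symptoms, the comparison that does not depend on the clinician's view of causality is the count by arm for each event term. Related events are listed at any frequency, but that listing depends on the attribution. An event can be graded unrelated when "the event is attributed to an alternative etiology" (Protocol 8.2), and in sickle cell pregnancy another explanation will often be at hand for symptoms such as headache, nausea or dizziness. If such events were frequent, the literal rule would give them no row of their own by arm.

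**Working it through.** **Inputs.** Threshold 0.5% (SAP 8.1). Population: all randomised women (SAP 5.2.1). Planned number 476 (SAP 3.1 and 4; Protocol 3.1).

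**The plan's own total.** 396 × 1.20 = 475.2, rounded up to 476. This matches the stated figure.

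**Threshold as a count.** 0.005 × 476 = 2.38 women.

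| Women with the event | Percent of 476 | Row if the rule is a ceiling | Row if the rule is a minimum |
|---|---|---|---|
| 1 | 1/476 = 0.21% | yes | no |
| 2 | 2/476 = 0.42% | yes | no |
| 3 | 3/476 = 0.63% | no | yes |
| more than 3 | above 0.63% | no | yes |

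At 476 the two readings select sets of terms that do not overlap.

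**Sensitivity to the denominator.** The literal rule drops terms seen in three or more women for any number from 400 (0.5% = 2.0) to 599 (0.5% = 2.995). At 396 women 0.5% is 1.98, so the literal rule would already drop terms seen in two, and a minimum would keep them. The cut-off expressed as a count is therefore not fixed.

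**Which reading the documents support.**
- In SAP 8.1 the related-event sentence says 'also' and waives frequency. That works as an exception to a rule that screens out rare events. It makes little sense as an exception to a rule that screens out frequent ones.
- The percentage rule in SAP 8.2 is a minimum.
- Protocol 8.3 promises a summary of all adverse events. SAP 12.1, which gives only the main changes from the protocol, does not withdraw this.

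All three point to a minimum.

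**What the literal rule would leave out.** Start from terms seen in three or more women and remove what is shown elsewhere:
1. Events graded related, at any frequency (SAP 8.1). The bar for 'possibly related' is low: "Onset of the AE has a reasonable temporal relationship to study product administration and a causal relationship is not biologically implausible" (Protocol 8.2).
2. Serious events (SAP 8.2). The follow-up e-CRF (Protocol Appendix 07) labels its top severity grade 'Severe (SAE)', so where the form is followed, severe events go to the SAE tables.
3. Named endpoints (SAP 2.2, 7.2.2 and 7.2.3).

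This leaves non-serious events, mainly mild or moderate, that are graded unrelated and are not endpoints. Protocol 8.1 names 20 symptoms to be sought at each visit. One of them, epigastric pain, is also named in SAP 2.2 item 7, though that list is open-ended. The other 20 − 1 = 19 can fall in the gap when they are non-serious and graded unrelated.

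**The case against.** The strongest reply is that this is an evident slip. The surrounding text points to a minimum, any competent analyst would read it so, and under that reading the frequent events are tabulated. SAP 11 adds an independent check of code and output. Much of this stands, and it is why the point is minor. It does not make the edit unnecessary. The SAP is the specification against which the checker works, and the two readings give tables with no event terms in common.

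A reader might infer that the plan hides common adverse events, or that such events would have no by-arm reporting at all. The documents do not support that:
- The 'Total' row of Table shell 5 has by-arm columns and most naturally counts women with any adverse event. The possible loss is the breakdown by term. The row is undefined, however, so this cannot be taken as settled.
- Protocol 8.3 remains in force, and Protocol 8.6 ties adverse-event monitoring to the two treatment groups. Protocol 8.3 does not itself say that the summary is by arm.
- Related, serious and endpoint events are shown whatever their frequency.

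Nor can one say that SAP 8.1 is the only route to a by-arm display. SAP 6.3 promises summaries of concurrent illnesses and medical conditions, and SAP 6 says that summary tables will be given for each treatment. SAP 6.3 does not say whether it covers events arising during the study, so it narrows the gap without closing it.

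**Conclusion.** The rule is wrong as written and should be corrected. Followed literally at 476 women, it gives by-arm rows only to terms seen in one or two women. Terms seen in three or more that are non-serious, graded unrelated and not named endpoints would lose their per-term row by arm, although they may still be counted in an aggregate total. The direction of the slip is clear from the documents.

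The size is modest: one part of the safety tables, with no effect on any efficacy estimate, test, population or data collection. The documents give no adverse-event rates, so the number of terms affected cannot be stated.

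The conclusion assumes that the study population in SAP 8.1 means all randomised women and that about 476 are randomised. The restriction to mild or moderate events assumes that sites use the severity label on the follow-up e-CRF as printed; Protocol 8.3 records severity and seriousness as separate items.

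**What to change.** - In SAP 8.1 replace 'up to 0.5%' with 'at least 0.5%'. Keep it as a percentage and do not write in a count, because three women is the cut-off at 476 but two at 396. Dropping the threshold altogether would serve equally well.
- Define the 'Total' row of Table shell 5 as the number and percentage of women with any adverse event, by arm. Rarer terms are then still counted and the commitment in Protocol 8.3 is met.
- Keep the listing of related events at any frequency as it stands.

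The cost is one phrase, one row definition and perhaps a longer table, with no new data. Make the edit before unblinding and record it under SAP 12.2, so that the choice of reading is documented before results by arm are seen.
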